##### 7.1.1.2 Serum bile acid responder endpoint

In the primary analysis of the fasting bile acid responder endpoint, dropouts and treatment completers with a missing average at the end of the treatment will be treated as non-responders. Patients in need of surgical rescue (i.e., biliary diversion and/or liver transplant) will be classified as non-responders.

As a sensitivity analysis, a tipping point analysis of fasting bile acid responder endpoint will be performed to evaluate the strength of evidence if the result is significant. The details of this are addressed in the Section 8.6.3.1.

## 8 STATISTICAL METHODS

### 8.1 General statistical conventions

All personnel involved with the analysis of the study will remain blinded until database lock. For DSMB analyses see Section 8.9.2. All statistical procedures will be completed using SAS® version 9.4 or higher.

Statistical testing for each primary endpoint analysis will be performed with a 1-sided overall Type I error rate of 0.025, adjusting for 2 comparisons between each active arm vs. the control. All other secondary endpoints for treatment comparisons will not be adjusted for multiplicity and nominal p values will be provided. Two-sided 95% confidence intervals (CI) will be provided when relevant.

For analysis adjusting for stratification factors (PFIC type and age category), if a patient is under 6 months due to imputed birth date ([Appendix A](#)), then the patient will be grouped to the age category ‘6 months to 5 years’.

Continuous variables will be summarized using descriptive statistics, including the number of patients with non-missing value (n), mean, median, SD, minimum and maximum. “n” will be presented without a decimal point, minimum and maximum values will be presented in the same precision as in the database, mean and median will be presented in one more decimal place than the minimum and maximum, and SD will be presented in one more decimal place than the mean and median.

For categorical variables, summaries will include counts of patients (frequencies) and percentages. Percentages will be rounded to one decimal place. Descriptive summaries of change from baseline in categorical variables will be provided using shift tables, if applicable.

For summary purposes, if not otherwise specified, the baseline value of a parameter is defined as the last non-missing assessment of that parameter prior to the first intake of study drug ([Appendix A](#)). Derived variables used for the analyses are provided in [Appendix A](#). All summaries will be presented by treatment group, unless otherwise specified.

For summary tables, the following 2 presentations will be used:

- For baseline related tables and protocol deviations: odevixibat 40 µg/kg/day, odevixibat 120 µg/kg/day, odevixibat 2 doses combined, placebo, and overall (3 treatment groups combined) will be presented.
- For the safety and efficacy related tables: odevixibat 40 µg/kg/day, odevixibat 120 µg/kg/day, odevixibat 2 doses combined, and placebo will be presented.

The visit window details for the derivation of study weeks and time points are outlined in [Appendix B](#).

All patient data, including those derived, will be presented in individual patient data listings. All

listings will be sorted by patient ID, treatment group, date/time and visit. Each patient's sex and age will be stated on each listing. Data listings will be based on all randomized patients.

## 8.2 Subject disposition

All patients who provided informed consent will be included in a summary of patient accountability.

The following categories will be summarized (by treatment group and overall where applicable):

- Patients screened
- Screening failures
- Patients randomized
- Patients randomized from Study [A4250-003](#)
- Patients randomized and dosed
- Patients completing treatment
- Patients completing the study
- Patients discontinuing treatment (including reasons for treatment discontinuation)
- Patients withdrawing early from study (including withdrawal reasons)
- Patients entering the extension study (A4250-008)

Additionally, patients included in the FAS analysis set will be summarized by region ([Appendix C](#)).

## 8.3 Protocol deviations

Important protocol deviations will be identified prior to database lock. All exclusions of patients from the per-protocol (PP) analysis sets will be performed programmatically using the criteria of important protocol deviations (Section [6.3](#)) in a blinded way and reviewed at the final protocol deviations review meeting prior to the final database lock, through clinical input provided by the sponsor, using the following sources of information:

- Supportive subject listings, provided by the [REDACTED] lead statistician ahead of the protocol deviation review meeting, based on data recorded on the eCRF.
- Protocol deviation logs, provided by [REDACTED] Clinical, Pharmacovigilance, Medical and Data Management.

The number of patients with identified important protocol deviations will be summarized by treatment group and overall (on randomized patients). Details on important protocol deviations will be provided in a listing on all randomized patients.

In addition, a listing will be provided with all protocol deviations identified based on data recorded on the eCRF and/or protocol deviation logs from [REDACTED] Medical and Data Management (on randomized patients) prior to database lock and documented in the CSR.

## 8.4 Demographics and baseline characteristics

### 8.4.1 Demographics

Age, height, weight and BMI at baseline and other demographic variables e.g., age category (6 months to 5 years, 6 to 12 years, and 13 to 18 years), sex, race, ethnicity, country, and region (see [Appendix C](#)) will be summarized by treatment group and overall descriptively using the FAS analysis set.

### 8.4.2 Baseline and disease characteristics

The following disease characteristics will be summarized by treatment group and overall: years since PFIC diagnosis, type of PFIC, presence of significant pruritus per investigator report, at least one s-BA level >100  $\mu\text{mol/L}$  within 6 months prior to screening visit, reason for discontinuation of historical PFIC related investigational medications, and diagnostic genetic laboratory test as well as Child-Pugh classification and hepatic impairment classification per NCI Organ Dysfunction Working Group for the FAS analysis set.

Child-Pugh classification: mild (Class A), moderate (Class B), or severe hepatic impairment (Class C) is based on the FDA Guidance for Pharmacokinetics in Patients with Impaired Hepatic Function. Determination of the classification is made based on medical review of baseline laboratory data and medical history.

Hepatic impairment will also be classified per the NCI Organ Dysfunction Working Group classification as mild, moderate or severe (Mansfield et al. 2016 [10]). Both the Child-Pugh and NCI classification will be included in the baseline characteristics and both will be applied in the subgroup analysis based on hepatic impairment status.

The following continuous parameters will also be summarized: estimated glomerular filtration rate (eGFR); baseline Z-score (weight, height, and BMI); and baseline values of alanine aminotransferase (ALT); aspartate aminotransferase (AST); gamma-glutamyl transferase (GGT); total bilirubin; alkaline phosphatase; INR; and vitamins A, E, and 25 hydroxy D.

eGFR will be calculated based on the modified/bedside Schwartz equation. For patients <18 year of age, Bedside Schwartz Equation will be used:

$$\text{GFR (mL/min/1.73 m}^2\text{)} = (36.2 \times \text{Height in cm}) / \text{Creatinine in } \mu\text{mol/L}$$

For patients  $\geq 18$  years, the isotope dilution mass spectrometry (IDMS)-traceable Modification of Diet in Renal Disease (MDRD) Study equation will be used:

$$\text{GFR (mL/min/1.73 m}^2\text{)} = 175 \times (\text{Creatinine in } \mu\text{mol/L}/88.4)^{-1.154} \times (\text{Age})^{-0.203} \times (0.742 \text{ if female}) \times (1.212 \text{ if African American})$$

A listing will be created to present all the demographic and baseline characteristics for the FAS analysis set. In addition, an individual listing on liver biopsies performed within 1 year prior to screening will be produced.

The results of pathologic variants identified for ATP8B1 or ABCB11 genes will be listed for all patients for the FAS analysis set.

### 8.4.3 Medical and surgical history

The frequencies and percentages of patients with reported medical and surgical history will be presented by system organ class (SOC) and preferred term (PT) by treatment group and overall for the SAF analysis set. Medical and surgical history will be coded using MedDRA version 23.0 throughout the study. The summary table will be sorted alphabetically for SOC and PT. Medical and surgical history will also be listed.

### 8.4.4 Prior and concomitant medications

Prior and concomitant medications used in this study will be coded using the version of the World Health Organization Drug Global Dictionary March 2020 throughout the study.

**Prior medications:** All medications taken by a patient within 3 months prior to the first intake of study drug with a recorded medication stop date prior to the first intake of study drug are regarded as prior medication. This will not include historical PFIC related investigational medications collected separately on CRFs.

**Concomitant medications:** All medications taken by a patient on or after the first intake of study drug and medications with start date before the first intake of study drug without a recorded stop date prior to the first intake of study drug.

Prior and concomitant medication use during the study will be summarized descriptively using frequency tables by Anatomical Therapeutic Chemical (ATC) class 4 and preferred term (PT) by treatment group for the SAF analysis set. ATC class and PT will be presented alphabetically. All prior and concomitant medication will be listed. Details for imputing missing or partial start and/or stop dates of non-study medication are described in [Appendix D](#).

## 8.5 Extent of exposure

### 8.5.1 Treatment duration

Exposure will be summarized with descriptive statistics (n, mean, SD, minimum, median, and maximum) and presented by treatment group using the SAF analysis set. The exposure of study drug will be derived as follows:

Duration of exposure (in weeks) = (Date of last study drug intake – Date of first study drug intake + 1)/7.

Investigators are allowed to interrupt the study drug to allow adverse events to resolve, if necessary. Any drug interruption will not be considered when calculating the treatment duration.

### 8.5.2 Study drug compliance

Study drug compliance will be assessed by maintaining adequate study drug dispensing records. The study drug compliance over the treatment period will be calculated using 2 sources of data.

#### Source Data from CRFs

Treatment Compliance =  $100 \times [(\text{Number of capsules dispensed} - \text{number of capsules returned}) / \text{number of capsules that should have been taken}]$ .

The number of capsules that should have been taken is calculated as the number of days that the patient was in the treatment period (exposure as above) multiplied by the number of prescribed capsules to be taken (based on patient's body weight, [protocol Table 2](#)) during the treatment period. The total number of capsules actually taken is the total number of capsules recorded as taken based on the CRF (number of capsules dispensed minus returned) summed over the treatment period. If the number of capsules not returned is confirmed as missing and the study drug is confirmed as not having been returned, the derivation will not be done.

#### Source Data from eDiary

Treatment Compliance =  $100 \times (\text{total number of capsules taken} / \text{total number of capsules planned to be taken})$ . The number of capsules planned to be taken will be estimated based on patient's body weight at Visit 3 and Visit 6 per [protocol Table 2](#). The number of capsules planned to be taken before Visit 6 will be the same as the number estimated at Visit 3, and after Visit 6 will be the same as the number estimated at Visit 6.

The calculated compliance rates will be summarized and the one based on CRFs data will be considered the primary compliance rate. The compliance rates reported by visit on the CRFs will be summarized also.

Descriptive summary statistics will be used to summarize study drug compliance by treatment group. The number and percentage of patients with compliance <80%, between 80% and 120%, and >120% will also be presented based on the SAF analysis set.

## 8.6 Efficacy analyses

This section addresses the analyses to be conducted on the primary, secondary, and exploratory efficacy variables. The primary objective of this study is to demonstrate the efficacy of repeated daily doses of 40 µg/kg/day and 120 µg/kg/day of odevixibat in children with progressive familial intrahepatic cholestasis (PFIC) Types 1 and 2, as determined by the following:

- Proportion of patients experiencing at least a 70% reduction in fasting serum bile acid (s-BA)

concentration from baseline to end of treatment or reaching a level  $\leq 70$   $\mu\text{mol/L}$  compared to placebo after 24 weeks of treatment

- The proportion of positive pruritus assessments at the subject level over the 24-week Treatment Period

The efficacy analysis will be carried out using the patients from the FAS and/or PP analysis set, unless otherwise specified. Figures for selected efficacy endpoints, such as the primary pruritus endpoint, change in s-BA, change in other patient reported and caregiver reported outcomes, will be provided by treatment group and by visit.

For efficacy endpoints derived from central laboratory data, if central laboratory data are not available due to COVID-19 or other reasons, local laboratory data will be used.

## 8.6.1 Analyses methods

### 8.6.1.1 Cochran Mantel Haenszel (CMH) Test

The CMH test is used in the analysis of stratified categorical data. It tests the association between treatment and a binary outcome such as responder while considering the stratification factors. For the proportion of patients experiencing at least a 70% reduction in fasting s-BA concentration from baseline to the end of treatment or reaching a level  $\leq 70$   $\mu\text{mol/L}$  after 24 weeks of treatment, the CMH test will be used for treatment comparisons. CMH stratified by PFIC type and age category will be performed to compare the proportion of the responders in fasting bile acid at the end of treatment (based on average of Weeks 22 and 24). The testing procedure is addressed in the Section [8.6.1.3](#).

In the CMH test, data in a stratum will not be used in the calculation of the p-value if a row sum or column sum is 0 in the contingency table. To ensure that all data are used when this occurs, data will be pooled with the adjacent age stratum that has a smaller number of subjects. If a row sum or column sum is still 0 after pooling data, all age groups will be pooled (i.e. the CMH test will be stratified by PFIC type only). If a row sum or column sum is still 0, the CMH test will not be stratified. Pooling strategy will also be conducted for a stratum with  $< 4$  patients.

The proportion together with corresponding Clopper-Pearson exact 95% CI, odds ratio and corresponding 95% CI, and p-value for the CMH test will be presented. The proportion difference with corresponding exact unconditional 95% CI without adjusting stratification factors will be presented. Miettinen-Nurminen (score) CI with adjusting stratification factors will be reported for common risk difference (i.e., proportion difference). The exact CI will be reported for the common odds ratio by using an algorithm based on Vollset, Hirji, and Elashoff (1991) [[11](#)]. SAS code will be found in [Appendix E](#).

### 8.6.1.2 Analysis of Covariance (ANCOVA) model

The ANCOVA model is usually used to test the main and interaction effects of categorical variables on a continuous dependent variable, controlling for the covariates. The ANCOVA model will be used to analyze the comparisons of the proportion of positive pruritus assessments

at subject level over the 24-week treatment period between the treatment groups.

### 8.6.1.3 Multiplicity

For EU and RoW, the primary analysis will be related to the serum bile acid responder endpoint. For US, the primary analysis will be related to the pruritus endpoint. For each primary endpoint, a pooled analysis for the closed testing procedure will be applied to control the 1-sided overall type I error rate for two treatment comparisons vs. the placebo at the 0.025 level as specified below:

In the closed testing procedure, the low and high dose groups are pooled to compare with the placebo group first. If the 1-sided p-value is  $\leq 0.025$ , the 1-sided p-values for low dose vs. placebo and high dose vs. placebo, respectively will be calculated. If both individual p-values are  $\leq 0.025$ , a significant treatment effect will be declared on both dose groups. If only one of them is  $\leq 0.025$ , a significant treatment effect will be declared on the corresponding dose group.

In testing the primary endpoint for US, treatment arms will be separated in the pooled analysis and the "lsmestimate" statement in SAS Proc Mixed will be used to compare pooled active arms vs. the placebo. See [Appendix E](#).

Adjusted p-values will also be reported when unadjusted p-values are presented directly from the model. The adjusted p-value for an individual dose is calculated as the maximum value of the unadjusted p-value for the pooled low and high doses and the unadjusted p-value for the individual doses.

Analyses of secondary and exploratory endpoints will provide supportive efficacy and safety information regarding the differences between the treatment groups. No adjustments will be performed for multiple comparisons when testing these secondary and exploratory endpoints.

### 8.6.2 Treatment by center interaction analysis (multi-center study)

There will be only a few patients per center, so no direct exploration of treatment-by-center interaction effect is planned. Additional treatment-by-covariate interactions may be explored.

### 8.6.3 Analyses of primary efficacy endpoints

The primary analyses on the primary endpoints will be based on the FAS. Additional analyses on the primary endpoints will be conducted for PP analysis set.

For EU and RoW, proportion of patients experiencing at least a 70% reduction in fasting s-BA concentration from baseline to the end of treatment or reaching a level  $\leq 70$   $\mu\text{mol/L}$  after 24 weeks of treatment will be analyzed using the CMH test. Patients with missing data at the end of treatment will be classified as non-responders. CMH stratified by PFIC type and age category will be performed to compare the proportion of the responders in fasting bile acid at the end of treatment (based on average of Weeks 22 and 24). The testing procedure is addressed in the Section 8.6.1.3. The contrasts of primary interest will be the treatment differences at end of treatment (Week 22 and 24); also, the difference at Week 4, Week 8, Week 12, and Week 18 will

be estimated and analyzed.

For US, the primary endpoint is the proportion of positive pruritus assessments at the subject level over the 24-week Treatment Period. A positive pruritus assessment is defined as a scratching score of  $\leq 1$  or at least a one-point drop from baseline on the Albireo ObsRO instrument. At each assessment, the AM score will be compared to the baseline AM average, and the PM score will be compared to the baseline PM average. Both AM and PM pruritus assessments will be included in the analysis of this endpoint. For analysis purposes, diary entries will be assigned to a study day based on the recorded date regardless of recorded time. AM scores from the period of 14 days prior to or on the first dose day of study medication will be averaged as AM baseline. PM scores from the period of 14 days prior to the first dose day of study medication will be averaged as PM baseline. Baseline score will be rounded to an integer to evaluate the positive pruritus assessments for the primary analysis. Additional analysis will be conducted using unrounded baseline score.

An ANCOVA model will be used for treatment comparisons. The model will include treatment arm, AM baseline pruritus score, PM baseline pruritus score, and stratification factors, i.e., PFIC type and age category. The testing procedure is addressed in the section [8.6.1.3](#).

LS mean (SE) by treatment arm and LS mean difference (SE), 95% confidence intervals, and p-values (where applicable) between treatments vs. placebo will be provided (see Section [8.6.1.3](#) below). SAS code will be found in [Appendix E](#). If there are concerns on model assumptions, normality will be checked based on Shapiro-Wilk test and homogeneity of variances will be checked based on Levene's test. For normality testing, Shapiro-Wilk test will be performed for each arm. The p-value from each arm will be combined to get an overall p-value based on Fisher's combined probability test.

A non-parametric ANCOVA based on the rank scores will be used as a sensitivity analysis to calculate the p-values. The proportion of positive pruritus assessments at subject level over 24-week treatment period will be ranked ignoring treatment group. The value of midranks will be used in the case of ties. The baseline pruritus scores will also be ranked in the same manner.

### **8.6.3.1 Sensitivity and supportive analyses of primary efficacy endpoints**

#### **EU and RoW primary endpoint**

- A sensitivity analysis will be performed by excluding patients whose baseline value is  $\leq 70$   $\mu\text{mol/L}$  using the same approach as for the primary analysis.
- Logistic regression will be performed as a supportive analysis for this endpoint. The model will include treatment arm, baseline value, and stratification factors, i.e., PFIC type and age category. If the logistic model cannot converge, then the age category with small sample size may be pooled to handle the convergence of the modeling.

- A tipping point analysis will be conducted to evaluate the influence of missing data at the end of treatment. To start, one patient on placebo arm with a missing value at the end of treatment is assumed as a responder and the primary analysis will be re-run to see if the active treatment group is still significantly better compared to the placebo arm. This will be performed for each patient on placebo arm with a missing value at the end of treatment to see how the result changes, and the worst result will be reported for this step (i.e. the worst scenario). If the result is still significant then this process will continue by assuming any 2 patients on placebo arm with missing values as responders until the result becomes non-significant.

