## 3 STUDY DESIGN

### 3.1 General study design

This is a double-blind, randomized, placebo-controlled, Phase 3 study to investigate the efficacy and safety of 40 µg/kg/day and 120 µg/kg/day of odevixibat compared to placebo in children with PFIC Type 1 and 2.

The study includes a 35- to 56-day Screening Period followed by a 24-week Treatment Period and a 4-week Follow-Up Period. After completion of the Screening Period, eligible patients (20 per treatment group) will be randomized on Day 0 (Visit 3) in a 1:1:1 fashion to receive 40 µg/kg/day or 120 µg/kg/day of odevixibat, or a matching placebo. Study data will be periodically reviewed by an unblinded Data Safety and Monitoring Board (DSMB).

A total of approximately 60 patients with a clinical diagnosis of PFIC Type 1 or 2 that have been genetically confirmed will be randomized. The randomization will be done in blocks and stratified according to PFIC type (Type 1 and 2) and age category (6 months to 5 years, 6 to 12 years, and 13 to ≤18 years) to ensure approximate balance between dose schemes (1:1:1).

The study will target 15% of enrolled patients to be PFIC-1 patients. If enrollment of all PFIC-2 patients is completed and the 15% enrollment of PFIC-1 patients has not yet been achieved, then enrollment of PFIC-2 patients will continue to reach the total study target enrollment. An attempt will be made to randomize a minimum of 10 patients from each age category (6 months to 5 years, 6 to 12 years, and 13 to ≤18 years). A maximum of 5 patients that were treated in Study [A4250-003](#) will be allowed to participate in this study.

Patients who complete the Treatment Period and Visit 9 (Day 168, Week 24) in this study will be invited to participate in a 72-week open-label extension study ([A4250-008](#), EudraCT Number 2017-002325-38, subject to a separate study approval) in which all patients will receive odevixibat 120 µg/kg/day. Prior to [protocol amendment 6](#), patients who had completed at least 12 weeks of the Treatment Period and had either no improvement or intolerable symptoms were eligible to complete the End of Treatment (EOT) Visit and were offered the opportunity to enter Study [A4250-008](#).

There will be up to 10 clinic visits during the study and one scheduled telephone contact, as follows:

- Visit 1: Screening Period start. Patient is considered enrolled after signing the informed consent form (ICF) (Days -56 to -35)
- Visit 2: Screening Visit 2 (Days -28 to -7)

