## 5 SAMPLE SIZE AND POWER

For the EU and RoW, the primary analysis will be related to the serum bile acid responder endpoint. For the US, the primary analysis will be related to the pruritus endpoint. The CMH test stratified by randomization strata will be used to test the serum bile acid responder endpoint. The individual null hypothesis is that the odds ratio of the response in an active arm vs. placebo is 1. The alternative hypothesis is that the odds ratio is greater than 1. An ANCOVA will be used for treatment comparisons for the proportion of positive pruritus assessments at subject level. The individual null hypothesis is that the average proportion of positive assessments is the same between the active and placebo arms. The alternative hypothesis is that the average proportion is larger in the active arm.

Since each active arm will be compared with the placebo, there will be two individual null hypotheses for each endpoint. In each endpoint, a pooled analysis for the closed testing procedure will be applied to control the 1-sided overall type I error rate for the two odevixibat treatment comparisons vs. placebo at the 0.025 level [6,7,8]. The significance of an active arm will be claimed if both 1-sided p-values in the pooled analysis and individual treatment comparison are less than or equal to 0.025.

The study will enroll 60 to 70 patients in order to obtain at least 20 evaluable patients in each arm. For each primary endpoint, simulations with 5,000 iterations using 20 patients per arm were conducted to estimate the power after multiplicity adjustment, resulting in a standard error (SE) of <0.7% for each estimated power.

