Based on the Phase 2 study (A4250-003) data, both low and high dose groups are assumed to have the same positive treatment effects in both the serum bile acid and pruritus endpoints in the simulation. For serum bile acids, binomial distributions were used to simulate the proportion of responders to estimate the power. The simulated proportions were analyzed using the Cochran-Mantel-Haenszel (CMH) test to generate the following 1-sided p-values: both odevixibat arms pooled vs. placebo, low dose vs. placebo, and high dose vs. placebo. Assuming 60% responders in the odevixibat arms and 10% responders in the placebo arm, the power to claim significance for a particular odevixibat arm after multiplicity adjustment is approximately 94%. The probability to claim significance for at least one arm, and for both arms are approximately 99% and 91%, respectively. If the response rates are 50% in the odevixibat arms and 10% in the placebo arm, with 20 patients per arm, the probability to claim significance for a particular odevixibat arm after multiplicity adjustment is approximately 82%. The probability to claim significance for at least one arm, and for both arms is approximately 91% and 73%, respectively.

For the proportion of positive pruritus assessments at the subject level in pruritus scores, beta-binomial distributions were used for power simulations since the binary results of the individual assessments within a subject are likely correlated [9]. The effect size was 1.0526 from the original sample size calculation using change from baseline as the endpoint. The same effect size was assumed for the current endpoint for the low and high dose vs. the control. A difference of 15%, 20%, 25%, and 30% in proportion of positive pruritus assessments were considered in power simulation. Within each difference, proportions of positive assessments in the placebo arm ranging from 15% to 35% were considered. Subsequently, the proportion of positive

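### The age-pooling fallback for the supportive s-BA logistic regression does not cover the most probable separation pattern, an arm of placebo patients with no responder (about 12% under the plan's own assumptions)

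*SAP*

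**What the plan says.** Under the EU and RoW primary endpoint, SAP section 8.6.3.1 plans a supportive logistic regression of s-BA response on treatment arm, baseline value, PFIC type and age category. If the model cannot converge, "then the age category with small sample size may be pooled to handle the convergence of the modeling". No penalised, exact or profile-likelihood method is named for this model.

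Section 5 gives the planning inputs: "Assuming 60% responders in the odevixibat arms and 10% responders in the placebo arm", with a second scenario, "If the response rates are 50% in the odevixibat arms and 10% in the placebo arm, with 20 patients per arm". On size, "The study will enroll 60 to 70 patients in order to obtain at least 20 evaluable patients in each arm", which is about 20 to 23 per arm at 1:1:1. Section 7.1.1.2 adds that "dropouts and treatment completers with a missing average at the end of the treatment will be treated as non-responders".

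The primary analysis is the stratified CMH test. For it, section 8.6.1.1 sets out a stepwise rule for pooling strata with a zero row or column sum, and an exact confidence interval for the common odds ratio.

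**The concern.** The plan expects only 2 placebo responders (20 × 0.10). If there are none, treatment arm itself separates the data: the likelihood keeps rising as the placebo log odds go to minus infinity. Age plays no part in this, so pooling age categories cannot remove it.

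The rule is loose in two further ways. It applies only when the model fails to converge, whereas under separation a program may stop and print a huge estimate and standard error without clearly failing. It is also permissive, and it gives no cut-off for a small category.

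At stake is the one specified s-BA responder analysis that adjusts for baseline s-BA. If the case arose, the replacement method would have to be chosen after unblinding.

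**Working it through.** **Inputs from the SAP.** Placebo rate 10%; active rate 60% or 50%; 20 per arm in the power simulation; 60 to 70 patients in total; 1:1:1 allocation; one-sided 0.025 with the pooled comparison tested first; PFIC-1 target 15% (section 3.1). Age mix, baseline s-BA values and the example data sets below are assumptions, because the SAP gives none.

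**1. Reproduce the plan's power.** Binomial simulation (400,000 runs), unstratified CMH without continuity correction, closed test:

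| Scenario | Particular arm | At least one arm | Both arms |
|---|---|---|---|
| 60% vs 10%, SAP | 94% | 99% | 91% |
| 60% vs 10%, recomputed | 94.9% | 98.3% | 91.5% |
| 50% vs 10%, SAP | 82% | 91% | 73% |
| 50% vs 10%, recomputed | 82.1% | 90.8% | 73.5% |

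Agreement is within one percentage point, so the inputs have been read correctly.

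**2. Probability of no placebo responder.** P = (1 − p)^n.

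- Plan's rate, n = 20: 0.9^20 = 12.2%.
- Plan's rate, n = 23: 0.9^23 = 8.9%.
- Assumed rates not in the SAP, n = 20: 15% gives 3.9%; 5% gives 35.8%; 3% gives 54.4%; 2% gives 66.8%.
- P reaches one half at p = 1 − 0.5^(1/20) = 3.4%.

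**3. Other separation patterns** (simulated, 60 patients, placebo 10%, active 60% or 50%).

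- An age level with all or no responders: below 0.1% with equal age groups, up to about 2.7% with an assumed uneven age mix (60/23/17%) and a 50% active rate.
- PFIC-1 with all or no responders: about 2.1% to 3.5%.

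No placebo responder is therefore the leading pattern, and age separation, which pooling can cure, is the rarer one.

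**4. Effect of pooling age.** One constructed data set: 0/20 on placebo, 12/20 in each active arm, Newton-Raphson logistic fit. Active-versus-placebo log odds ratio (SE) by number of iterations:

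| Age in model | 8 | 15 | 25 |
|---|---|---|---|
| 3 levels | 9.71 (21.7) | 16.71 (719) | 26.71 (106,762) |
| 2 levels | 9.71 (21.7) | 16.71 (719) | 26.71 (106,771) |
| Dropped | 9.66 (21.9) | 16.66 (725) | 26.66 (107,620) |

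The estimate grows by about 1 per iteration in every row. What is printed depends on where the program stops, not on age.

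**5. Comparison fits.** Firth on the same data is finite: 4.06 (SE 1.46), 4.13 (1.50) and 4.14 (1.52) in the three rows. With 1 or 2 placebo responders the ordinary fit with three age levels is stable without pooling: 3.56 (SE 1.2) and 2.79 (SE 0.9).

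**The case against.** **The event is not probable.** At the only placebo rate in the SAP, at least one placebo patient responds about 88% of the time (91% with 23 per arm), and the ordinary model can then generally be fitted. This stands. A reader might infer that the logistic model is likely to fail or will give no usable treatment estimate. The SAP does not support that: it would need a placebo rate below about 3.4%, which the SAP nowhere states. Counting missing values as non-response could lower the placebo rate, but the SAP does not say whether its 10% already allows for this.

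**PFIC type.** A reader might also infer that the small PFIC-1 group creates the same problem. It does not. In a main-effects model all PFIC-1 patients across the three arms (15% of 60 = 9) would have to share one outcome. With 6 active and 3 placebo, the chance that none responds is 0.4^6 × 0.9^3 = 0.3%, or 0.5^6 × 0.9^3 = 1.1% at a 50% active rate. The infinite coefficient would then be the one for PFIC type, and the treatment estimate need not be lost.

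**Something survives even at 0/20.** The likelihood-ratio test and lower profile-likelihood bound remain finite under ordinary maximum likelihood. Unadjusted, 12/20 versus 0/20 gives a chi-square of 21.9 and a lower 95% bound of about 12.5 on the odds ratio. This is correct, but the SAP does not specify those outputs for this model, and there is still no point estimate.

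**Little depends on it.** The analysis is supportive. The CMH test gives a p-value with no placebo responders, its exact odds-ratio interval is already specified, and section 8.6.4 has an MMRM for s-BA change with a baseline term. This stands and limits the weight of the point. The MMRM analyses change, not response, so it is not a full substitute.

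**Conclusion.** The point holds in a limited form. The stated fallback cannot repair the most probable separation pattern, which has about a 12% chance at the SAP's 10% placebo rate with 20 per arm (9% with 23). If it occurs, the treatment log odds ratio and Wald interval from this model are unusable whatever is done with age, and the non-convergence trigger may not reveal it. The primary conclusion is not at risk.

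The 12% rests on the SAP's own rate and arm size, and on independent patients with a common placebo rate. The figures at other placebo rates, the ranking against age separation under uneven ages, and the example fits rest on assumptions labelled as such above. That pooling age cannot help when no placebo patient responds follows from the form of the model and does not depend on the example data.

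**What to change.** In section 8.6.3.1, state that if separation is detected (including an arm with no responders) or the model does not converge, the same model (treatment arm, baseline s-BA, PFIC type, age category) will be fitted by Firth penalised likelihood, with profile-likelihood confidence intervals and tests. The age-pooling sentence may remain for sparse age levels, where it can help.

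The cost is one added sentence and one option in the procedure call. The penalised estimate is shrunk somewhat towards zero, but only when the fallback is used; the ordinary fit stays in place otherwise.
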